#### 7.1.2 Secondary Efficacy Endpoints

The secondary efficacy endpoints comparing FX006 to placebo for each of the shoulder conditions (glenohumeral OA and shoulder AC) in this study include the following:

- Change from Baseline in the weekly mean of the average daily shoulder pain with movement score at Week 12
- Change from Baseline in the SPADI pain subscale at Week 12
- Change from Baseline in the SPADI disability subscale at Week 12
- The PGIC score at Week 12
- Change from Baseline in the ROM of external rotation at Week 12

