### **9.1 General Considerations and Methods**

Data collected in this study will be presented using summary tables, figures, and patient data listings. Summary tables will present data by treatment group and, if applicable, by time of collection. Continuous variables will be summarized using descriptive statistics, specifically the mean, median, standard deviation, minimum, and maximum. Categorical variables will be summarized by frequencies and percentages. Figures will be used to support the presentation of certain data. Sensitivity analyses may be performed to examine the effect of missing data, as well as the effect of Baseline imbalance, should it occur.

All confidence intervals (CIs), statistical tests, and resulting p-values will be reported as 2-sided. Multiplicity will be addressed by analyzing the key secondary endpoints sequentially in the order presented in the protocol, testing each endpoint at the nominal  $\alpha = 0.05$ , 2-sided level to ensure overall type I error control at the 2-sided 0.05 level.

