## 9.4 Statistical Methods

### 9.4.1 Analysis of Efficacy

#### 9.4.1.1 Primary efficacy analyses

For each shoulder condition, the primary AUC endpoint will be calculated and comparisons will be estimated from an Analysis of Covariance model with parameters for treatment group, Baseline average daily shoulder pain with movement score, and analysis site. In addition, the model for shoulder AC will also include a covariate for pain duration since onset. Full details of the AUC analyses will be detailed in the SAP.

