#### 9.4.1.2 Secondary efficacy analyses

The key secondary change from Baseline endpoints will be analyzed with longitudinal mixed models for repeated measures with fixed effects for treatment group, study week, treatment-by-week interaction, analysis site, and Baseline score. Patient will be the random effect. Treatment differences from control will be estimated via LSMs from the analysis model along with 95% CIs and associated 2-sided p-values. This model assumes data are missing at random and includes only observed data. In addition, the model for shoulder AC will also include a covariate for pain duration since onset.

Multiplicity will be addressed by analyzing the key secondary endpoints sequentially in the order presented in the protocol, testing each endpoint at the nominal  $\alpha = 0.05$ , 2-sided level to ensure overall type I error control at the 2-sided 0.05 level.

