#### 9.4.1.3 Exploratory efficacy analyses

Area under the curve and continuous exploratory efficacy endpoints will be analyzed similarly to the primary and key secondary endpoints for each shoulder condition. Categorical endpoints will be compared via chi-square or exact tests depending on incidence rates. No adjustments will be made for multiplicity for exploratory efficacy endpoints.

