#### 9.4.6 Sample Size Determination

Approximately 250 patients will be randomized in a 1:1 ratio to either FX006 or placebo (approximately 136 patients with glenohumeral OA and approximately 114 patients with shoulder AC). Sample sizes were estimated to yield a statistically significant difference ( $\alpha = 0.05$ , 2-sided) between the FX006 and placebo groups in the average daily shoulder pain with movement score at Week 12 (the first secondary endpoint for each shoulder condition). For glenohumeral OA, the true difference between the groups was assumed to be 1, with a standard deviation of 2, based on data observed in knee OA studies of FX006 and taking into consideration the clinical significance of a 1-point difference between the treatment groups. For shoulder AC, the true difference between the groups was assumed to be 1.2, with a standard deviation of 2.1, based on a review of the existing literature. The primary endpoint analyzing the AUC for the weekly mean of the average daily shoulder pain with movement score over 8 weeks should, therefore, have >80% power to show a significant difference between the FX006 and placebo groups. As the 2 shoulder conditions (glenohumeral OA and shoulder AC) are combined into 1 protocol strictly for ease of administration, all statistical testing will be performed separately for each shoulder condition and the overall type I error rate will be controlled at the  $\alpha = 0.05$  level within each shoulder condition.

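### The key secondary test sequence is not conditional on the primary AUC test, so the rule as written does not hold overall type I error at 0.05 within a shoulder condition

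*Combined protocol and SAP*

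**What the plan says.** The multiplicity rule appears in the same words in the synopsis (Statistical Analyses), Section 9.1 and Section 9.4.1.2: "Multiplicity will be addressed by analyzing the key secondary endpoints sequentially in the order presented in the protocol". Each endpoint is tested at nominal 0.05, and the purpose is given as "to ensure overall type I error control at the 2-sided 0.05 level".

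Section 7.1.2 lists five secondary endpoints. The first is "Change from Baseline in the weekly mean of the average daily shoulder pain with movement score at Week 12". SPADI pain, SPADI disability, PGIC and external rotation follow, all at Week 12.

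The primary endpoint is the 8-week AUC of the same diary pain score. Section 9.4.1.1 says only that "comparisons will be estimated from an Analysis of Covariance model" and names the covariates. It does not connect that test to the secondary sequence.

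Section 9.4.6 sets the scope of the error claim: "all statistical testing will be performed separately for each shoulder condition and the overall type I error rate will be controlled at the" 0.05 level inside each condition. Section 9.4.1.3 takes the exploratory endpoints out of the claim: "No adjustments will be made for multiplicity for exploratory efficacy endpoints".

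Section 9 promises a SAP before database lock. The document supplied contains no SAP text that completes the rule.

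**The concern.** Putting endpoints in order does not by itself protect the error rate. In a fixed-sequence procedure the protection comes from two conditions: a test is opened only if every earlier test was significant, and the chain starts with the primary. The second condition is not written anywhere. The first is at best implied by the word sequentially.

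What is at stake is the status of a secondary result when the primary fails. If the AUC test misses and Week 12 pain gives p<0.05, the plan does not say whether that finding is confirmatory or nominal, and the question could end up being settled after unblinding. The two tests also differ in time window (8 weeks against Week 12) and in model (analysis of covariance against a mixed model for repeated measures), so they need not agree.

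**Working it through.** **Inputs, per shoulder condition**
- One primary test (Section 9.4.1.1). The plan states no alpha for it separately; 2-sided 0.05 is taken from Section 9.4.6.
- Five secondary tests (Section 7.1.2), each at 2-sided 0.05 (Section 9.4.1.2). The term key secondary is not defined against that list; all five are taken as key.
- Correlation between test statistics: not given in the documents. Values from 0 to 0.9 are assumed, equal across all pairs.
- Each test rejects if |Z| > 1.96. All figures are for the global null (no true effect on any of the six endpoints).

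**Step 1. The plan's own figure.** Put the primary first, then the five secondaries in order, each tested only if all earlier ones were significant. Under the global null, any false positive requires the first test to be falsely significant:

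P(at least one false positive) = P(|Z1| > 1.96) = 0.05.

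A simulation of 1,000,000 draws gave 0.0496 to 0.0502 across the assumed correlations. So 0.05 is reproduced, but only with a primary gate and a stop rule.

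**Step 2. Stopping among secondaries, no primary gate.** A false positive now arises if the primary is falsely significant, or if the first secondary is, since the secondary chain can start without the primary:

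P(primary or first secondary) = 0.05 + 0.05 − P(both).

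With independence, P(both) = 0.05 × 0.05 = 0.0025, so the result is 0.10 − 0.0025 = 0.0975. With correlation, P(both) comes from the bivariate normal distribution.

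**Step 3. No stopping at all.** Any of the six tests may be falsely significant. With independence: 1 − 0.95^6 = 1 − 0.735 = 0.265. With correlation, the value comes from the six-variable normal distribution.

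| Assumed correlation | P(both), primary and first secondary | Step 2: stop rule, no primary gate | Step 3: no stop rule, six tests |
|---|---|---|---|
| 0 | 0.0025 | 0.0975 | 0.265 |
| 0.3 | 0.005 | 0.095 | 0.241 |
| 0.5 | 0.009 | 0.091 | 0.207 |
| 0.7 | 0.017 | 0.083 | 0.164 |
| 0.9 | 0.030 | 0.070 | 0.108 |

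In Step 2 the result falls to 0.05 only as the correlation approaches 1, where the two tests become the same test.

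**Step 4. Which family the claim covers.** Taken alone, the five secondaries with a stop rule are held at 0.05. Section 9.4.6 claims more than that: its statement is about all testing within a condition, so the primary belongs to the family and Step 2 is the relevant figure.

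**The case against.** The strongest defence is that full alpha at each step, a fixed order and a stated purpose of error control together describe fixed-sequence testing, and that without stopping the word sequentially would do no work. I accept this. Stopping among the secondaries is very probably intended, and the Step 3 figures are not a fair description of the plan.

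It can also be said that a primary endpoint conventionally opens the sequence, and that a SAP is still to come. Both make it likely that the intent is sound. Neither puts the gate in the text: the sentence sequences the key secondary endpoints, the primary is not among them, and Section 9 does not specifically defer the multiplicity rule to the SAP.

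Two stronger readings are tempting and are not supported:
- A reader might infer that the wording authorises a claim on Week 12 pain after a failed primary. It does not. Such a claim would conflict with the commitment in Section 9.4.6. The text leaves the mechanism incomplete; it grants no permission.
- A reader might infer that this outcome is likely because Section 9.4.6 sizes the trial on Week 12 pain and not on the AUC. Sizing on one endpoint does not show that the other is weaker. The same section expects more than 80% power for the AUC, and Section 1.3.3 reports a knee effect that was present at Week 1, grew through Week 7 and lasted to at least Week 16. The documents give no basis for a probability of AUC failure with Week 12 success.

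The two pain endpoints come from the same diary in the same patients, so independence is the least plausible case. That moves the excess towards the lower end of the range. It does not remove it.

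**Conclusion.** Wrong as written. With the secondaries read charitably as a fixed sequence with stopping, the primary and the first secondary are still two entry points at full 0.05. The familywise error within a condition is about 7.0% to 9.75% under the global null, against the claimed 5%. The range rests on assumed correlations of 0.9 to 0 and on the primary being tested at 0.05.

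The excess needs both the primary null and a secondary null to be true. If the primary effect is real, a stopping sequence of secondaries holds 0.05. The 10.8% to 26.5% range applies only if no stop rule is used. It is a worst case, and a reader should not take it as the plan's error rate.

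This is an incomplete rule attached to an explicit claim, not evidence that the trial will be analysed wrongly. It is more than missing detail, because it decides what may be concluded after a failed primary. Phase 2 status does not excuse it: the plan chose to claim control and waived adjustment only for exploratory endpoints. Separate use of 0.05 in each shoulder condition is declared by design and is not part of this point.

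**What to change.** In the synopsis, Section 9.1, Section 9.4.1.2 and the SAP, before unblinding, state the following:

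> Within each shoulder condition, the primary AUC endpoint is tested at 2-sided 0.05. The first key secondary endpoint is tested at 2-sided 0.05 only if the primary is significant, and each later one only if the primary and all preceding key secondaries are significant. After the first result with p ≥ 0.05, all later p-values in the sequence are nominal.

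Say also that the key secondary endpoints are the five in Section 7.1.2, in that order, if that is what is meant.

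With this wording the familywise error per condition is at most 0.05, whatever the correlation. Sample size, models, endpoints and data collection stay as they are. The only cost is the option to claim a secondary after a failed primary. If the gate was always intended, nothing is lost.

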#### 9.4.1.3 Exploratory efficacy analyses

Area under the curve and continuous exploratory efficacy endpoints will be analyzed similarly to the primary and key secondary endpoints for each shoulder condition. Categorical endpoints will be compared via chi-square or exact tests depending on incidence rates. No adjustments will be made for multiplicity for exploratory efficacy endpoints.

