### 5.3 Randomization and Blinding

Patients from each shoulder condition will be randomized on Day 1 to 1 of 2 treatment arms (FX006 or placebo) using centralized randomization accessed through an interactive voice/web response system randomization (IxRS) module.

Glenohumeral OA patients will be stratified by the Baseline average daily shoulder pain with movement score (0 to 10 NRS) (5.0 to <7.0 or ≥7.0 to 9.0). Shoulder AC patients will be stratified by the Baseline average daily shoulder pain with movement score (0 to 10 NRS) (5.0 to <7.0 or ≥7.0 to 9.0) and pain duration since onset at Screening (1 to 3 months, inclusive, or >3 to ≤6 months).

The blinded-assessor technique will be used in this study to maintain double-blind conditions. Key study site staff roles are defined below and a site-specific blinding plan will be developed to ensure the blind is maintained throughout the duration of the study. Treatments will be prepared by an unblinded pharmacist/coordinator who has experience with the preparation of study medication and who has been properly trained by the Sponsor or designee. Intra-articular injections will be performed by an unblinded injector.

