#### 7.1.3 Exploratory Efficacy Endpoints

The exploratory efficacy endpoints comparing FX006 to placebo for each of the shoulder conditions (glenohumeral OA and shoulder AC) in this study include the following:

- AUC of change from Baseline in the weekly mean of the average daily shoulder pain with movement score over Weeks 4, 12, 16, 20, and 24
- AUC of change from Baseline in the SPADI pain subscale over Weeks 4, 8, 12, 16, 20, and 24
- AUC of change from Baseline in the SPADI disability subscale over Weeks 4, 8, 12, 16, 20, and 24
- Change from Baseline in the weekly mean of the average daily shoulder pain with movement score at Weeks 1, 4, 8, 16, 20, and 24
- Change from Baseline in the SPADI pain subscale at Weeks 1, 4, 8, 16, 20, and 24
- Change from Baseline in the SPADI disability subscale at Weeks 1, 4, 8, 16, 20, and 24
- Change from Baseline in the SPADI total score at Weeks 1, 4, 8, 12, 16, 20, and 24
- The PGIC score at Weeks 1, 4, 8, 16, 20, and 24
- Change from Baseline in the ROM of external and internal rotation, abduction and flexion at Weeks 4, 8, 16, 20, and 24
- Change from Baseline in the ROM of internal rotation, abduction and flexion at Week 12
- Change from Baseline in the ASES pain subscale at Weeks 1, 4, 8, 12, 16, 20, and 24

- Change from Baseline in the ASES disability subscale at Weeks 1, 4, 8, 12, 16, 20, and 24
- Change from Baseline in the ASES total score at Weeks 1, 4, 8, 12, 16, 20, and 24
- Percent of responders based on the SPADI at Weeks 1, 4, 8, 12, 16, 20, and 24
- Proportion of patients experiencing a  $\geq 20\%$ ,  $\geq 30\%$ , or  $\geq 50\%$  decrease in the weekly mean of the average daily shoulder pain with movement score at Weeks 1, 4, 8, 12, 16, 20, and 24
- Change from Baseline in average weekly rescue medication use
- Change from Baseline in the average weekly SI score
- Change from Baseline in the EQ-5D-5L at Weeks 1, 4, 8, 12, 16, 20, and 24

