#### 9.4.5 Subgroups and Covariates

Preplanned subgroup analyses including aspiration status, OA grade based on the Samilson-Prieto classification system, gender, and Baseline average daily shoulder pain with movement score will be detailed in the SAP. In addition, subgroups of pain duration since onset are preplanned for shoulder AC patients. Further subgroups may be defined and explored after all preplanned analyses have been completed to further elucidate study results.

Covariates for efficacy analyses will include Baseline average daily shoulder pain with movement score, Baseline score for the endpoint, analysis site, and, for AC patients, pain duration since onset. Other covariates may be explored and will be fully defined in the SAP.

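### Exploratory responder endpoints are tested without the randomisation strata or Baseline covariates; the test is valid, but it gives up some power if the strata predict response

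*Combined protocol and SAP*

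**What the plan says.** Protocol 9.4.1.3 sends AUC and continuous exploratory endpoints to the same kind of model as the primary and key secondary endpoints. For the rest it says: "Categorical endpoints will be compared via chi-square or exact tests depending on incidence rates". No strata, covariates, effect estimate or confidence interval are named. The same section adds: "No adjustments will be made for multiplicity for exploratory efficacy endpoints".

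The endpoints concerned are in 7.1.3: the proportions with at least a 20%, 30% or 50% decrease in weekly mean pain, and "Percent of responders based on the SPADI at Weeks 1, 4, 8, 12, 16, 20, and 24". The pain responder rates are assessed at the same seven visits.

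On randomisation, 5.3 says: "Glenohumeral OA patients will be stratified by the Baseline average daily shoulder pain with movement score". There are two classes, 5.0 to <7.0 and 7.0 to 9.0. For AC it adds pain duration at Screening (1 to 3 months, or >3 to 6 months). That makes two strata in OA and four in AC.

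On adjustment, 9.4.5 says: "Covariates for efficacy analyses will include Baseline average daily shoulder pain with movement score, Baseline score for the endpoint, analysis site", and for AC also pain duration. The sentence does not separate continuous from categorical endpoints. The primary ANCOVA (9.4.1.1) and the secondary repeated-measures models (9.4.1.2) carry Baseline and site terms, plus pain duration in AC.

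**The concern.** The same weekly pain score is adjusted for Baseline when analysed as a continuous change and left unadjusted when cut into responder and non-responder. No reason is given.

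When allocation is balanced within strata that predict the outcome, part of the patient-to-patient variation can no longer contribute to the difference between arms. An unstratified chi-square test still counts that part in its variance. Its p-values are then somewhat too large and some power is lost.

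The gap between 9.4.1.3 and 9.4.5 also leaves room to choose adjusted or unadjusted responder p-values later. That choice would span three pain cut-offs and the SPADI responder at seven visits, with no multiplicity adjustment.

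**Working it through.** **The plan's own figure.** Section 9.4.6 claims >80% power. It sizes the trial on Week 12 pain; no responder endpoint has a stated rate or power. With power = Φ(δ / (σ√(2/n)) − 1.96):
- OA, n = 68 per arm (136/2), δ = 1, σ = 2: standard error 2√(2/68) = 0.343, 1/0.343 = 2.915, Φ(0.955) = 83.0%.
- AC, n = 57 per arm (114/2), δ = 1.2, σ = 2.1: standard error 2.1√(2/57) = 0.393, 1.2/0.393 = 3.051, Φ(1.091) = 86.2%.

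The claim reproduces, but it says nothing about responder rates.

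**Why stratification can matter.** The chi-square test uses variance p̄(1 − p̄)·2/n. Take two equal strata with response p̄ ± g/2 and 1:1 allocation within each. The difference between arms then varies only with p̄(1 − p̄) − (g/2)². At p̄ = 0.5 the ratio of the two variances is 1 − g², and a nominal 5% test has actual size 2{1 − Φ(1.96/√(1 − g²))}:
- g = 0.2: ratio 0.96, size 0.045
- g = 0.3: ratio 0.91, size 0.040
- g = 0.4: ratio 0.84, size 0.032
- g = 0.5: ratio 0.75, size 0.024

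If g = 0 there is no loss.

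**Simulation over assumed stratum gaps.** 40,000 trials per setting, exact 1:1 allocation within equal or near-equal strata, 50% overall response under the null. OA: 68 per arm, two strata, 38% vs 62% under the alternative. AC: 57 per arm, four strata, 37% vs 63%, with the gap measured from lowest to highest stratum. CMH is the stratified Cochran-Mantel-Haenszel test. All response rates and gaps are assumptions. Gains are taken from unrounded values.

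| Setting | Type I error, chi-square / CMH | Power, chi-square / CMH | Gain (points) |
|---|---|---|---|
| OA, gap 0 | 0.045 / 0.045 | 80.5% / 80.5% | 0 |
| OA, gap 20 | 0.043 / 0.047 | 80.9% / 81.8% | 0.9 |
| OA, gap 30 | 0.039 / 0.050 | 81.6% / 84.5% | 2.9 |
| OA, gap 40 | 0.032 / 0.051 | 82.3% / 87.4% | 5.0 |
| OA, gap 50 | 0.024 / 0.052 | 84.2% / 91.5% | 7.3 |
| AC, spread 20 | 0.046 / 0.048 | 80.2% / 80.5% | 0.3 |
| AC, spread 40 | 0.039 / 0.048 | 81.3% / 84.0% | 2.7 |

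**Simulation tied to the protocol's OA assumptions.** Change from Baseline has SD 2 and treatment difference 1 (9.4.6). Assumed: Baseline mean 6.8 and SD 1, limited to 5 to 9; mean placebo change −2; slope of change on Baseline from 0 to −1. 20,000 trials per setting, for the 20%, 30% and 50% responders.
- The gap in placebo response, high minus low Baseline stratum, ran from about −12 to +25 points. The percent decrease has Baseline in its denominator, so the gap can shrink or reverse.
- Type I error was 0.043 to 0.052 for chi-square and 0.046 to 0.052 for CMH.
- The power gain from CMH ran from about nil to 2.4 points. The largest was for the 30% responder at slope −1: 68.0% to 70.4%.

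**The exact test.** With no stratum effect at all, Fisher's test had type I error of about 0.030 in OA and 0.032 in AC, and power 5 to 6 points below chi-square. That comes mainly from its discreteness, not from the missing strata.

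**The case against.** The strongest reply is that this is a common and valid choice for exploratory endpoints, and that 9.4.1.3 is the specific rule while 9.4.5 is a general list. The list cannot mean every covariate in every analysis: it includes the Baseline score for the endpoint, and a responder indicator has none. This stands in part. A reader might infer a flat contradiction between the two sections; the text supports only an inconsistency that needs aligning.

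A reader might also infer that the planned tests are bound to be conservative and underpowered. The documents do not support that. They give no response rates by stratum, and under the protocol's OA assumptions the loss is nil to small. The simulations also favour stratification: they impose exact balance within strata and no dropout, while the documents state neither block size nor dropout rate. Less balance among analysed patients would weaken the conservatism.

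It is fair, too, that no decision depends on these tests, and that 9.4.1.3 specifies no interval, so nothing can be said about the width of planned intervals. Site is a listed covariate but not a stratification factor, so it bears on the inconsistency and not on the conservatism.

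What remains is that the strata are known and recorded, the other efficacy models adjust, and no reason is given for leaving responders out.

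**Conclusion.** The point holds as a minor improvement. The planned test is valid, and the primary endpoint and ordered secondary endpoints are untouched.

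The cost of leaving out the strata is conditional on their predicting response:
- about 0 to 2.4 points of power in the model using the protocol's OA difference and SD, which still needs assumed Baseline, placebo-change and slope values;
- about 3 to 7 points in OA only under assumed stratum gaps of 30 to 50 points;
- in AC, about 3 points at an assumed 40-point spread.

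The protocol-based model covers OA percent-decrease responders only. It does not cover AC pain duration, which is not in the denominator, or the SPADI responder, for which 7.2.7 gives no separate criterion.

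A reader who took this as a threat to the trial's conclusions would go beyond the documents. The inconsistency between 9.4.1.3 and 9.4.5 needs no assumption and is worth settling before unblinding.

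**What to change.** In 9.4.1.3, replace the sentence on categorical endpoints with one named method: responder endpoints are compared within each shoulder condition by a Cochran-Mantel-Haenszel test stratified by the randomisation factors (Baseline pain class; for AC also pain duration class), with the exact stratified version when counts are small. Report a stratified risk difference with its 95% CI.

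In 9.4.5, state which covariates apply to categorical endpoints. This is needed as well, because a test stratified by the randomisation factors still leaves out site and the Baseline endpoint score. Limiting 9.4.5 to continuous endpoints would cure the wording alone but would not recover any power.

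The cost is a few sentences and no new data. The one downside is that the four AC strata, with about 57 patients per arm in all (on average 57/4, about 14 per arm per stratum), may be sparse when response rates are low.
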